6.2. Treatment Period

After signed the ICF within 28 days, the eligible subjects must start treatment as soon as possible. For all subsequent visits, an administrative window of \pm 3 days is permitted, otherwise specified.

Subjects will receive a single dose of ATG-008 on Day -1, followed by a 48-hour observation for PK sample collection.

- Oral daily dosing of 15 mg or 30 mg begin on Day 1 and will continue in 28-day cycles
- It is planned that approximately 20 subjects will receive oral ATG-008 at an initial dose of 45 mg/QD and another 20 subjects will receive oral ATG-008 at an initial dose of 20 mg/BID. The 28 continuous days are regarded as one treatment cycle. The pharmacokinetic (PK) samples will be collected from 10 subjects each in the two dose groups.

The subjects will continue to use ATG-008 until radiologic disease progression, intolerable toxicities, or withdrawal of consent for further dosing (in which case subjects will continue to be followed for further anticancer treatment and survival status unless consent for this has been explicitly withdrawn). Subjects will fast ≥ 6 hours before those clinical visits which require evaluation of PK and fasting chemistry examination. PK, safety and tolerability for the 30-mg dose level will follow the assessment of the 15-mg dose level if DLTs occur in less than 2 of 6 subjects at the 15-mg dose level who complete Cycle 1.

The following evaluations will be performed at the frequency specified in the Table of Events, [Table 3](#). The evaluations should be performed prior to dosing on the visit day, unless otherwise specified.

- Adverse event evaluation (continuously)
- Concomitant medications evaluation (including medications for best supportive care)
- Concomitant procedures evaluation
- ECOG performance status
- Vital signs, weight
- Hematology laboratory
- Coagulation panel
- Fasting chemistry laboratory
- Special chemistry laboratory
- HbA1c
- Urine routine
- AFP
- HBV viral load (in subjects with positive HBsAg, HBeAg HBcAb or positive viral load at screening).
- Urine β -hCG (females of childbearing potential (FCBP) only)
- Radiologic response assessment/tumor evaluation and assessment of disease progression (see Section 6.4)

- PK sampling (see Section 6.5)

Detailed evaluations are listed in [Table 3](#).

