6.4. Response Assessments

Tumor response assessments should be performed in Screening (up to 28 days before the start of study drug) and every 8 weeks (\pm 5 days) from the first dose date until disease progression, death or withdrawal of consent from additional follow-up procedures. Tumor

assessments includes imaging (CT or MRI) of the chest, abdomen and pelvis at baseline. Subjects with brain lesions will have brain scans at screening and at each tumor assessment. After Screening, tumor assessments will be performed on completion of C2, C4 and C6 (i.e., C3, 5 and 7/Day1±7 days) using the same scanning modalities used at baseline. Corticosteroids (if used) dosage must be stable \geq 5 days prior to all scans. EOT scan need not be repeated if prior scan was $<$ 28 days.

If a subject discontinues study drug due to toxicity, subject or physician decision, the collection of response assessments should continue at the same schedule. Additionally, if a subject continues treatment beyond radiologic disease progression until symptomatic deterioration (see Appendix A, Section 19.1.2.4), tumor evaluations should continue until study drug is stopped. Evaluation of response should be performed using RECIST 1.1 guidelines.

New anticancer therapy includes any systemic medication, locoregional therapy, surgery, radiation or any other therapy intended to treat the subject's cancer.

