6.4.1 Assessment of Radiologic Response According to RECIST 1.1

Response will be assessed using RECIST 1.1 Appendix. Response assessments (tumor evaluations) include computed tomography (CT) scan or magnetic resonance imaging (MRI). The regions to be imaged are the chest, abdomen and pelvis, as well as any other region clinically indicated for tumor imaging. Subjects with brain metastases will have brain scans at Screening and at each tumor reassessment. The same mode of imaging for lesion evaluation at screening must be consistently used throughout the study.

The CT imaging should include contrast unless medically contraindicated. Conventional CT should be performed with contiguous cuts of 5 mm or less in slice thickness. Spiral CT should be performed by use of a 5 mm contiguous reconstruction algorithm.

All subjects with evidence of radiologic tumor response (CR or PR) should have the response confirmed with repeat assessments at the next scheduled scan, but after no less than 28 days. Response assessments must have occurred \geq 5 weeks from the first dose date to be considered as SD for a best response.

The Investigators will evaluate RECIST 1.1 response after each restaging and overall assessment. All related scans will be collected and saved for future independent central review.

If ORR of tumor is greater than 15% in the study dose group (45 mg/QD or 20 mg/BID), then this study will be expanded to enroll additional approximately 110 subjects using ORR as the primary study endpoint, to further evaluate the efficacy and safety of ATG-008.

All scans will be collected and then be reviewed centrally for independent analysis of ORR and other objective tumor response outcomes. mRECIST will then also be applied in tumor assessment, if necessary.

Additional details and definitions of response according to RECIST 1.1 are found in Appendix A in Section 19.1.

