10.3 Sample Size and Power Considerations

For the primary efficacy endpoint, ORR, the sample size is based on one-sample binomial test with normal approximation. The null hypothesis to be tested is that the ORR (defined as the proportion of subjects with at least a partial response (PR) based on the Treated population subjects) is $\leq 10\%$; the alternative hypothesis is that the ORR is $\geq 18\%$. With these hypotheses, a sample size of 130 (20+110) subjects in the Treated population would provide 80% power at a one-sided 0.025 significance level. This criterion requires that the lower limit of the 95% confidence interval (CI) for the ORR is greater than 10%.

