10.6.1 Analysis of the Primary Efficacy Endpoint

Overall response rate (ORR) is the primary efficacy endpoint. A responder is any subject who achieves a CR or PR. ORR is defined as the percentage of subjects that achieve a CR or PR.

ORR will be summarized with 95% confidence interval (CI), and tested using one sample binomial test for the Treated population analyzed in a similar way as for DCR. Subgroup analysis for ORR will be performed for subgroups specified in Section 10.6.3.

ORR with 95% confidence intervals will also be provided for the per-protocol population.

The primary analysis for ORR will be performed at approximately 3 months after the last subject is first dosed. All other endpoints will be analyzed at the same time. The analysis will be updated at 12 months after the last subject's first dose date.

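### The primary ORR cut-off at about 3 months precedes the week-16 scan, so the last-dosed subjects are tested on one scheduled post-baseline scan; the effect is small and depends on whether ORR must be confirmed

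*Combined protocol and SAP*

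**What the plan says.** - **Timing of the primary test (10.6.1):** "The primary analysis for ORR will be performed at approximately 3 months after the last subject is first dosed". The same section adds "The analysis will be updated at 12 months after the last" subject's first dose.
- **Scan schedule (6.4):** "Tumor response assessments should be performed in Screening (up to 28 days before the start of study drug) and every 8 weeks" (±5 days), counted from the first dose. The same section also ties scans to cycles: "tumor assessments will be performed on completion of C2, C4 and C6 (i.e., C3, 5 and 7/Day1±7 days".
- **First dose (6.2):** "Subjects will receive a single dose of ATG-008 on Day -1, followed by a 48-hour observation for PK sample collection". Continuous dosing starts on Day 1, so cycle-based dates can run about 2 days behind dates counted from the first dose.
- **Confirmation (6.4.1):** subjects with a CR or PR "should have the response confirmed with repeat assessments at the next scheduled scan, but after no less than 28 days".
- **Endpoint definition:** 10.6.1 says "A responder is any subject who achieves a CR or PR". Section 10.3 has ORR "defined as the proportion of subjects with at least a partial response (PR) based on the Treated population subjects". Section 3.1 likewise counts PR or CR. None of the three mentions confirmation.
- **Denominator (10.2.1):** everyone who received at least one dose.

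**The concern.** The analysis date and the scan calendar do not fit together. A response first seen at week 8 is to be confirmed at the next scheduled scan, which is week 16, but the primary test is run about three weeks before the last subject reaches week 16. The latest-dosed subjects count in full in the denominator and have had one scheduled chance to show a response, and no scheduled chance to have it confirmed.

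The possible cost is a lower observed ORR and lower power in the test that decides the trial. How much depends on something the protocol leaves open: whether the primary ORR is confirmed, and how a response still awaiting confirmation is counted at the cut-off.

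**Working it through.** **Inputs.** From 10.3: null 10%, alternative 18%, one-sided 0.025, n = 130 (20 + 110). From 10.1: expansion if ORR exceeds 15% in a dose group of about 20, that is at least 4/20. From 6.4 and 10.6.1: the dates above. Assumed: even accrual of the 110, because no rate is given for them. Two paces are used: 12 months (364 days), and 16.5 months (500.5 days), the latter being the pace of about 40 in 6 months in 4.3.

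**Step 1. The plan's own figure.** n = [1.960 × √(0.10 × 0.90) + 0.842 × √(0.18 × 0.82)]² / 0.08² = 129.8, so 130. The stated sample size reproduces (power 80.1% by the normal approximation).

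**Step 2. Calendar for the last subject.**

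| Event | Day from first dose |
|---|---|
| Scan 1 (week 8, ±5) | 51-61 |
| Primary cut-off (3 months) | about 91 |
| Scan 2 (week 16, ±5) | 107-117 |
| Scan 2 (C5 Day 1, ±7) | 105-119 |
| Latest scan 2, with cycles counted from Cycle 1 Day 1 (+2) | 121 |

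Even the earliest scan 2 is 105 − 91 = 14 days after the cut-off. The 28-day minimum alone could be met by day 79-89 (51 + 28 to 61 + 28), but only with an unscheduled scan.

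**Step 3. Subjects affected** = 110 × (scan day − 91) / accrual days.
- Day 112: 110 × 21/364 = 6.3, or 110 × 21/500.5 = 4.6.
- Over day 105-119: 4.2-8.5, or 3.1-6.2.
- Expected responders lost at 18%, if none of these subjects can count: 6.3 × 0.18 = 1.1, or 4.6 × 0.18 = 0.8, out of 130 × 0.18 = 23.4.

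**Step 4. Power if confirmation is required.** Success needs at least 20/130: z = (20/130 − 0.10)/√(0.09/130) = 2.05, while 19/130 gives 1.75. With k of the 110 unable to respond, unconditional power is P[Bin(130 − k, 0.18) ≥ 20]. Power given expansion conditions on at least 4 responders in the first 20, an event of probability 0.497 at 18%.

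| k | Unconditional | Given expansion |
|---|---|---|
| 0 | 0.812 | 0.901 |
| 3 | 0.778 | 0.878 |
| 5 | 0.754 | 0.860 |
| 6 | 0.740 | 0.850 |
| 8 | 0.713 | 0.830 |

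If the confidence interval is exact, the rule is at least 21/130 (lower limit 10.3%; 9.7% at 20). Power given expansion then falls from 0.849 to 0.794 (k = 5) or 0.782 (k = 6). Faster accrual makes the loss larger: 110 in 6 months gives about 12.5 affected at day 112, and unconditional power with k = 13 is 0.638.

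**Step 5. Power if any CR or PR counts.** Week-8 responses all count. Only a share s of responses, those first seen at week 16, is missed in the 5-6 affected subjects. With s = 10%, 25% and 50% (assumed), about 0.1, 0.2-0.3 and 0.5 responders are lost. Power given expansion is 0.897, 0.890-0.892 and 0.877-0.882, against 0.901.

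**Step 6. Type I error.** At a true ORR of 10%, P(≥20) is 0.034 with none excluded, and 0.024 and 0.022 with 5 and 6 excluded. The early cut-off lowers it.

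**The case against.** The strongest case is that the plan never says the primary ORR is confirmed. Three definitions count any CR or PR; confirmation appears only as a recommendation in the imaging section. TTR and DOR in 10.6.2 also start from the first documentation of response. On that endpoint every subject reaches the week-8 scan before day 91. The only timing evidence in the protocol also favours early responses: 1.4.1 reports that all three PRs in the earlier HCC cohort were met at the first restaging, after 2 cycles. Section 10.1 leaves final methods to a separate SAP, which may settle the definition, and the 12-month update captures whatever the first analysis missed.

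Most of this stands. A reader might infer that late-dosed subjects cannot be responders at all, or that the primary test is badly underpowered. The documents do not support that. It would need confirmation to be required, the next scheduled scan to be read strictly, pending responses to be counted as failures, and an accrual rate the plan does not give. Nor can one infer a false-positive risk, since the shortfall only removes responders.

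What does not fall away is the calendar itself. It needs no accrual assumption and no view on confirmation. The 12-month analysis is an update, not the primary test.

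**Conclusion.** The concern holds as a scheduling mismatch of modest size. Subjects first dosed in about the last 3 weeks of accrual (2-4 weeks over the scan windows) are in the primary denominator with one scheduled post-baseline scan.

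- **If ORR is confirmed per 6.4.1:** with 5-6 of 110 affected and all counted as non-responders, unconditional power falls from 81% to 74-75%, below the 80% that 10.3 claims, or from 90% to 85-86% given expansion. This also assumes that all responses are first seen at week 8.
- **If ORR is any CR or PR, as written:** no week-8 response is lost, and power given expansion falls from 90.1% to about 88-90%.

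The effect is conservative, arises only if the trial expands, and is recoverable at 12 months. The size rests on the assumed accrual of 12 to 16.5 months. The sample size of 130 is right on its own formula.

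**What to change.** In 10.6.1, set the primary ORR cut-off at about 4 months, and at least 18 weeks (day 126), after the last subject's first dose. This covers the latest window end (day 121), so every subject can have the week-16 scan before the test. A week-8 response can then be confirmed on schedule. A response first seen at week 16 still cannot, because its next scheduled scan is week 24.

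At the same time, align 3.1, 10.3 and 10.6.1 with 6.4.1: say whether ORR is confirmed and how a response awaiting confirmation is counted. If it is confirmed, state that the 18% in 10.3 refers to confirmed responses.

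The cost is a primary readout about 4-5 weeks later and a sentence in each section, with no extra scans or patients. If confirmed ORR is chosen and the 18% was meant as unconfirmed, the sample size must be rechecked. With 5% or 10% of responses failing to confirm (assumed), ORR becomes 0.18 × 0.95 = 17.1% or 0.18 × 0.90 = 16.2%. Power at 130 is then 73% or 64% unconditionally, and 85% or 78% given expansion.

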10.6.2 Analysis of the Secondary Efficacy Endpoints

Overall Survival is defined as the time from the first dose date until death. A subject who has not been reported as a death will be censored at the last available date the subject is known to be alive, or the clinical cut-off date, whichever is earlier.

Time to progression (TTP) will be calculated as the time from the first dose date to disease progression. Subjects who do not have disease progression will be censored at the date of the last tumor assessment that the subject was progression free, or the clinical cutoff date, whichever is earlier.

Progression free survival (PFS) is defined as the time from the first dose date to the date of disease progression according to RECIST 1.1 or death (due to any cause) on or prior to the clinical cutoff date, whichever occurs earlier. Subjects who do not have disease progression or have not died will be censored at the date of the last tumor assessment that the subject was progression free on or prior to the clinical cutoff date.

Disease control rate (DCR) is defined as the percentage of subjects with complete (CR), or partial response (PR) or stable disease (SD).

For responders, time to response (TTR) and response duration will be analyzed.

TTR is the time from the first dose date to the first documentation of response of PR or better. TTR will be summarized for responders using summary statistics.

Duration of response (DOR) is defined as the time from the time when criteria are first met for CR/PR (whichever is first recorded) until the first date that recurrent or progressive disease is objectively documented for responders. DOR will be censored using the same censoring rules as used for PFS.

Survival rate is defined as the Kaplan-Meier estimated proportion of subjects surviving at 6, 9, 12 months.

10.6.3 Subgroup Analyses

The effect of treatment on the efficacy variable ORR, OS, PFS, TTP and DCR will be investigated within subgroups defined by the following baseline prognostic variables if the study is expanded:

- Age group (≤ 65 , > 65 years);
- Baseline ECOG Performance Status (0 or 1);
- Macroscopic vascular invasion (involvement of branches of portal or hepatic veins: yes or no);
- Extrahepatic spread (yes or no);

- Median baseline level of albumin ($>$ median or \leq median);
- Median baseline level of alkaline phosphatase ($>$ median or \leq median);
- Median baseline level of total bilirubin ($>$ median or \leq median);
- Prior systemic therapy (First line or more than first-line)
- Portal vein thrombosis (yes or no);
- AFP (\leq 400ug/L or $>$ 400ug/L)
- Liver involvement by HCC (\leq 50% or $>$ 50%)
- BCLC Stage (B or C);

The analysis methods described in previous sections will be used for each subgroup separately. A forest plot for subgroups will be also provided for the primary efficacy endpoint ORR.

10.6.4 PK analysis

Intensive PK modeling will be performed for ATG-008 and M1 on the plasma and urine concentration data. Descriptive statistics of model fitting and PK parameters will be summarized in appropriate tables and figures.

10.6.5 Exploratory Analyses

10.6.5.1 Evaluate Changes in AFP

An AFP response is defined as normalization or $>$ 50% decline from baseline. The AFP response rate is the percentage of subjects with baseline elevation in AFP who meet AFP response criteria. The response rate will be summarized descriptively.

10.6.5.2 Exposure-Response Analyses

Exploratory analyses may be conducted to evaluate the relationship between ATG-008 and M1 exposure and select response variables. Graphical exploration may initially be performed to identify significant trends between drug exposure and response. Depending on the findings, appropriate modeling and simulation may be conducted to quantify exposure-response relationships using pharmacostatistical modeling.

10.7 Safety Analysis

All safety results will be summarized for the Safety population.

Safety and tolerability will be monitored through continuous reporting of adverse events and serious adverse events, laboratory abnormalities, and incidence of subjects experiencing dose modifications, dose interruptions, and/or premature discontinuation of study drug. Data from all subjects who receive one or more doses of study drug will be included in the safety analyses. Adverse events, physical examination findings (including vital sign measurements), clinical laboratory information, ECG interpretations and concomitant medications/procedures will be tabulated and summarized by treatment arm. Descriptive statistics will be provided for both baseline and change from baseline of ECG values by treatment arm. All toxicities will be summarized by severity grade based on the CTCAE, Version 4.03, frequency and relationship to treatment. Adverse events will be coded according to the Medical Dictionary for Regulatory Affairs (MedDRA). Serious adverse events, AEs of interest, AEs Grade 3 or higher, and AEs leading to discontinuation or death will be summarized and listed separately.

11. ADVERSE EVENTS

11.1 Monitoring, Recording and Reporting of Adverse Events

An AE is any noxious, unintended, or untoward medical occurrence that may appear or worsen in a subject during the course of a trial. It may be a new intercurrent illness, a worsening concomitant illness, an injury, or any concurrent impairment of the subject's health, including laboratory test values (as specified by the criteria in Section 11.3), regardless of etiology. Any worsening (i.e., any clinically significant adverse change in the frequency or intensity of a pre-existing condition) should be considered an AE. A diagnosis or syndrome should be recorded on the AE page of the CRF rather than the individual signs or symptoms of the diagnosis or syndrome.

Clinically significant signs and symptoms associated with disease progression are expected to be reported as AEs; however progression of HCC (PD) that is asymptomatic or solely documented radiographically per RECIST 1.1 does not require reporting as an AE.

An overdose, accidental or intentional, whether or not it is associated with an AE, or abuse, withdrawal, sensitivity or toxicity to an investigational product should be reported as an AE. If an overdose is associated with an AE, the overdose and adverse event should be reported as separate terms. See Section 8.2.2 for the definition of overdose. In the event of overdose, the subject should be monitored as appropriate and should receive supportive measures as necessary. There is no known specific antidote for ATG-008 overdose. Actual treatment should depend on the severity of the clinical situation and the judgment and experience of the treating physician.

All subjects will be monitored for AEs during the trial. Assessments may include monitoring of any or all of the following parameters: The subject's clinical symptoms, laboratory, pathological, radiological or surgical findings, physical examination findings, or other appropriate tests and procedures.

All AEs and SAEs will be recorded by the Investigator from the time the subject signs informed consent to 28 days after the last dose of study drug. However serious adverse events made known to the Investigator at any time thereafter that are suspected of being related to study drug will also be reported. AEs and serious adverse events (SAEs) will be recorded on the AE page of the CRF and in the subject's source documents. All SAEs must be reported to Antengene Drug Safety or designee within 24 hours of the Investigator's knowledge of the event by facsimile, or other appropriate method, using the SAE Report Form, or approved equivalent form.

11.2 Evaluation of Adverse Events

A qualified Investigator will evaluate all adverse events as to:

11.2.1 Seriousness

An SAE is any AE occurring at any dose that:

- Results in death;
- Is life-threatening (i.e., in the opinion of the Investigator, the subject is at immediate risk of death from the AE);
- Requires inpatient hospitalization or prolongation of existing hospitalization (hospitalization is defined as an inpatient admission, regardless of length of stay);
- Results in persistent or significant disability/incapacity (a substantial disruption of the subject's ability to conduct normal life functions);
- Is a congenital anomaly/birth defect;

- Constitutes an important medical event.

Important medical events are defined as those occurrences that may not be immediately life threatening or result in death, hospitalization, or disability, but may jeopardize the subject or require medical or surgical intervention to prevent one of the other outcomes listed above.

Medical and scientific judgment should be exercised in deciding whether such an AE should be considered serious.

Events not considered to be SAEs are hospitalizations for:

- Routine treatment or monitoring of the studied indication not associated with any deterioration in condition.
- The administration of blood or platelet transfusion as routine treatment of studied indication. However, hospitalization or prolonged hospitalization for a complication of such transfusion is a reportable SAE.
- A procedure for protocol/disease-related investigations (e.g., surgery, scans, endoscopy, sampling for laboratory tests, bone marrow sampling). However, hospitalization or prolonged hospitalization for a complication of such procedures is a reportable SAE.
- Hospitalization or prolongation of hospitalization for technical, practical, or social reasons, in absence of an AE.
- A procedure that is planned (i.e., planned prior to starting of treatment on trial); must be documented in the source document and the CRF. Hospitalization or prolonged hospitalization for a complication from such a procedure is a reportable SAE.
- An elective treatment of a pre-existing condition unrelated to the studied indication.
- Emergency outpatient treatment or observation that does not result in admission, unless fulfilling other seriousness criteria above.

If an AE is considered serious, both the AE page/screen of the CRF and the SAE Report Form must be completed.

For each SAE, the Investigator will provide information on severity, start and stop dates, relationship to study drug, action taken regarding study drug, and outcome.

For death caused by study indication progression of disease (PD) will not be reported as SAE.

